3.2 Exclusion Criteria

3.21 Non-adenocarcinoma histology.

3.22 Adenocarcinoma originating in the ampulla or appendix. (Duodenal Tumors that involve the ampulla but originate in the duodenum are eligible).

3.23 Currently participating and receiving study therapy, or have participated in a study of an investigational agent and received study therapy, or used an investigational device ≤ 4 weeks of registration.

3.24 Diagnosis of immunodeficiency or be receiving systemic steroid therapy or any other form of immunosuppressive therapy ≤ 7 days prior to registration.

3.25 History of active TB (Bacillus Tuberculosis).

3.26 Hypersensitivity to pembrolizumab or any of its excipients.

3.27 Any of the following:

- Prior anti-cancer monoclonal antibody (mAb) ≤ 4 weeks prior to registration

3.28 Prior chemotherapy, targeted small molecule therapy, or radiation therapy ≤ 2 weeks prior to registration or who has not recovered to \leq Grade 1 or baseline from adverse events due to the previously administered agent.
 Note: Subjects with \leq Grade 2 neuropathy are an exception to this criterion and may qualify for the study.

3.29a Received major surgery ≤ 2 weeks prior to registration, subject must have recovered adequately from the toxicity and/or complications from the intervention prior to starting therapy.

3.29b Known additional malignancy that is progressing or requires active treatment or that may interfere with interpretation of response evaluation, in the judgment of the investigator.

3.29c Known active central nervous system (CNS) metastases and/or carcinomatous meningitis. Subjects with previously treated brain metastases may participate provided they are stable (without evidence of progression by imaging ≤ 4 weeks prior to registration and any neurologic symptoms have returned to baseline), have no evidence of new or enlarging brain metastases, and are not using steroids ≤ 7 days prior to registration. This exception does not include carcinomatous meningitis which is excluded regardless of clinical stability.

3.29d Active autoimmune disease (including but not limited to: patients with a history of inflammatory bowel disease, including ulcerative colitis and Crohn's Disease, patients with a history of symptomatic disease (e.g., rheumatoid arthritis, systemic progressive sclerosis [scleroderma], systemic lupus erythematosus, autoimmune vasculitis [e.g. Wegener's Granulomatosis]); CNS or motor neuropathy considered of autoimmune origin (e.g., Guillain-Barre Syndrome and Myasthenia Gravis, multiple sclerosis)) that has required systemic treatment in the past 2 years (i.e. with use of disease modifying agents, corticosteroids or immunosuppressive drugs). Replacement therapy (e.g., thyroxine, insulin, or physiologic corticosteroid replacement therapy for adrenal or pituitary insufficiency, etc.) is not considered a form of systemic treatment.

3.29e Known history of or any evidence of active, non-infectious pneumonitis.

3.29f Active infection requiring systemic therapy.

3.29g History or current evidence of any condition, therapy, or laboratory abnormality that might confound the results of the trial, interfere with the subject's participation for the full duration of the trial, or is not in the best interest of the subject to participate, in the opinion of the treating investigator.

3.29h Known psychiatric or substance abuse disorders that would interfere with cooperation with the requirements of the trial.

3.29i Pregnant or breastfeeding, or expecting to conceive or father children within the projected duration of the trial, starting with the pre-screening or screening visit through 120 days after the last dose of trial treatment.

3.29j Received prior therapy with an anti-PD-1, anti-PD-L1, or anti-PD-L2 agent, or other immune checkpoint inhibitor (e.g. anti-CTLA4).

3.29k History of Human Immunodeficiency Virus (HIV) (HIV 1/2 antibodies).

3.29l Known active Hepatitis B (e.g., HBsAg reactive) or Hepatitis C (e.g., HCV RNA [qualitative] is detected).

3.29m Received a live vaccine within 30 days of planned start of study therapy.
Note: Seasonal influenza vaccines for injection are generally inactivated flu vaccines and are allowed; however, intranasal influenza vaccines (e.g., Flu-Mist®) are live attenuated vaccines and are not allowed.

4.0 Test Schedule

Tests and procedures	Active Monitoring Phase			
	≤28 days prior to registration	Day 1 Cycle 1	Day 1 Cycles 2 -8 and beyond (+/-3 days)	End of treatment (PD, withdrawal, or removal ⁹) (+7days)
History and exam, wt, ECOG PS	X	X ^{6,8}	X ⁶	X
Height	X			
Adverse event assessment	X	X ⁸	X	X
Concomitant medication review	X	X ⁸	X	
Hematology: CBC/ differential	X	X	X	X
Chemistry: SGOT (AST), ALT, alk phos, T. bili, creatinine, calcium,, Na, K, glucose, LDH, bicarbonate, uric acid, Mg, Phosphorus, total protein, blood urea nitrogen, albumin	X	X	X	
PT/INR and aPTT	X			
Urinalysis ³	X			
T3, FT4 and TSH	X	X	X	
Tumor measurement (should include at least a CT of the abdomen/pelvis, and appropriate imaging of any other target site lesions) ^{1, 10}	X		X ⁵	X
CEA	X		X ⁷	X
Pregnancy test	X ²			
Mandatory blood sample (see Section 14.0) ⁸	X	X	X ⁴	X
Mandatory tissue sample (see Section 17.0)	X			

1. Use same imaging throughout the study.
2. For women of childbearing potential only. Must be done ≤7 days prior to registration.
3. Urine blood, glucose, protein, specific gravity. Microscopic exam if abnormalities on urinalysis results.
4. Collected cycles 2, 3, 4, 8 (see Section 14.0). Kits are required for this collection.
5. Every 4 cycles beginning with end of cycle 4, and at end of treatment.
6. Directed physical exam only.
7. Every even-numbered cycle, beginning with cycle 2, and at end of treatment.
8. ≤24 hours prior to treatment.
9. Continued study treatment beyond initial radiographic disease progression may be allowed; see Section 13.4 for details. These

patients would continue follow-up per test schedule until confirmed progression.

10. To be submitted <60 days after registration

R Research funded (see Section 19.0). Mandatory research blood draws should be collected and submitted *after* the patient is registered onto the study, but before beginning study treatment.

5.0 Grouping Factor

None

6.0 Registration Procedures

6.1 To register a patient, access the ACCRU web page at [REDACTED] go to the Application section and click on “Registration” and enter the registration/randomization application. The registration application is available 24 hours a day, 7 days a week. Back up and/or system support contact information is available on the Web site. If unable to access the Web site, call the Academic and Community Cancer Research United (ACCRU) Registration Office at [REDACTED] between the hours of 8 a.m. and 4:30 p.m. Central Time (Monday through Friday).

Instructions for the registration/randomization application are available on the above web page under the Study Resources section, “Application Training.”

Prior to initiation of protocol study intervention, this process must be completed in its entirety and an ACCRU subject ID number must be available as noted in the instructions. It is the responsibility of the individual and institution registering the patient to confirm the process has been successfully completed prior to release of the study agent. Patient registration via the registration application can be confirmed in any of the following ways:

- Contact the ACCRU Registration Office [REDACTED]. If the patient was fully registered, the Registration Office staff can access the information from the centralized database and confirm the registration.
- Refer to “Application Training” at [REDACTED]; click on “Registration, Installation & Entry Instructions.”

6.2 Correlative Research

A mandatory correlative research component is part of this study; the patient will be automatically registered onto this component (see Sections 3.17, 14.0 and 17.0).

6.3 Documentation of IRB approval

Documentation of IRB approval must be on file in the Registration Office before an investigator may register any patients. Approvals should be uploaded using the online ACCRU Regulatory Management System (ARMS).

In addition to submitting initial IRB approval documents, ongoing IRB approval documentation must be on file (no less than annually) with ACCRU. Approvals should be uploaded using the online [REDACTED]. If the necessary documentation is not submitted in advance of attempting patient registration, the registration will not be accepted and the patient may not be enrolled in the protocol until the situation is resolved.

Submission of annual IRB approvals is required until the study has been closed through your IRB.

6.4 Prior to accepting the registration, the registration/randomization, the registration/randomization application will verify the following:

- IRB approval at the registering institution
- Patient eligibility

- Existence of a signed consent form
- Existence of a signed authorization for use and disclosure of protected health information

6.5 At the time of registration, the following will be recorded:

- Patient has/not given permission to store and use his/her sample(s) for future research to learn about, prevent, or treat cancer.
- Patient has/not given permission to store and use his/her sample(s) for future research to learn, prevent, or treat other health problems (for example: diabetes, Alzheimer's disease, or heart disease).
- Patient has/not given permission for ACCRU to give his/her sample(s) to outside researchers.

6.6 Treatment cannot begin prior to registration and must begin ≤ 10 days after registration.

6.7 Pretreatment tests/procedures (see Section 4.0) must be completed within the guidelines specified on the test schedule.

6.8 All required baseline symptoms (see Section 10.5) must be documented and graded.

6.9a Treatment on this protocol must commence at an ACCRU institution under the supervision of a medical oncologist.

6.9b Study drug is available on site.

6.9c Blood draw kit is available on site.

7.0 Protocol Treatment

7.1 Treatment Schedule

Drug	Dose/Potency	Dose Frequency	Route of Administration	Regimen/Treatment Period	Use
Pembrolizumab	200 mg (flat dosing)	Q3W	IV infusion	Day 1 of each 3 week cycle	Experimental

Note: Trial treatment should begin ≤ 10 days after registration and as close as possible to the date on which treatment is allocated/assigned.

Note: Details on preparation and administration of pembrolizumab (MK-3475) are provided in section 15.0.

7.2 For this protocol, the patient must return to the consenting ACCRU institution for evaluation at least every 21 days (+/- 3 days) during treatment.

7.3 Dosing interruptions, not due to adverse effects.

Dosing interruptions are permitted in the case of medical / surgical events or logistical reasons not related to study therapy (e.g., elective surgery, unrelated medical events, patient vacation, and/or holidays). Subjects should be placed back on study therapy within 3 weeks of the scheduled interruption. The reason for interruption should be documented in the patient's study record.

7.4 Timing of Dose Administration

Trial treatment should be administered on Day 1 of each cycle after all procedures/assessments have been completed. Trial treatment may be administered up to 3 days before or after the scheduled Day 1 of each cycle due to administrative reasons.

7.5 Dose Administration

All trial treatments will be administered on an outpatient basis. Pembrolizumab 200 mg will be administered as a 30 minute IV infusion every 3 weeks. Sites should make every effort to target infusion timing to be as close to 30 minutes as possible. However, given the variability of infusion pumps from site to site, a window of -5 minutes and +10 minutes is permitted (i.e., infusion time is 30 minutes: -5 min/+10 min).

7.6 Treatment Continuation

To permit continued study treatment beyond initial radiographic disease progression the following will be required:

- a) The patient's performance status must be stable
- b) Clinical symptoms and signs of disease progression must be absent
- c) A repeat scan to assess for true disease progression must be performed in approximately 4 weeks
- d) Any patient with pending organ compromise must be discontinued from study treatment

Note: See section 13.4 for patients that have initial progression

7.7 Concomitant Medications/Vaccinations (allowed & prohibited)

Medications or vaccinations specifically prohibited in the exclusion criteria are not allowed during the ongoing trial. If there is a clinical indication for one of these or other medications or vaccinations specifically prohibited during the trial, discontinuation from trial therapy or vaccination may be required.

7.71 Acceptable Concomitant Medications

All treatments that the investigator considers necessary for a subject's welfare may be administered at the discretion of the investigator in keeping with the community standards of medical care. All concomitant medication will be recorded on the case report form (CRF) including all prescription, over-the-counter (OTC), herbal supplements, and IV medications and fluids. If changes occur during the trial period, documentation of drug dosage, frequency, route, and date may also be included on the CRF.

7.72 Prohibited Concomitant Medications

Subjects are prohibited from receiving the following therapies during the Screening and Treatment Phase (including retreatment for post-complete response relapse) of this trial:

- Antineoplastic systemic chemotherapy, biological therapy, immunotherapy, not specified in this protocol

- Investigational agents other than pembrolizumab
- Radiation therapy
 - Note: Radiation therapy to a symptomatic solitary lesion or to the brain may be allowed at the investigator's discretion.
- Live vaccines within 30 days prior to the first dose of trial treatment and while participating in the trial. Examples of live vaccines include, but are not limited to, the following: measles, mumps, rubella, varicella/zoster, yellow fever, rabies, BCG, and typhoid vaccine.
- Systemic glucocorticoids for any purpose other than to modulate symptoms from an event of clinical interest of suspected immunologic etiology. The use of physiologic doses of corticosteroids may be approved after consultation with the Sponsor.

Subjects who, in the assessment by the investigator, require the use of any of the aforementioned treatments for clinical management should be removed from the trial. Subjects may receive other medications that the investigator deems to be medically necessary.

The Exclusion Criteria describes other medications which are prohibited in this trial.

There are no prohibited therapies during event monitoring.

7.8 Diet/Activity/Other Considerations

7.81 Diet

Subjects should maintain a normal diet unless modifications are required to manage an AE such as diarrhea, nausea or vomiting.

7.82 Contraception

Pembrolizumab may have adverse effects on a fetus in utero. Furthermore, it is not known if pembrolizumab has transient adverse effects on the composition of sperm. Non-pregnant, non-breast-feeding women may be enrolled if they are willing to use 2 methods of birth control or are considered highly unlikely to conceive. Highly unlikely to conceive is defined as 1) surgically sterilized, or 2) postmenopausal (a woman who is ≥ 45 years of age and has not had menses for greater than 1 year will be considered postmenopausal), or 3) not heterosexually active for the duration of the study. The two birth control methods can be either two barrier methods, or a barrier method plus a hormonal method to prevent pregnancy. Subjects should start using birth control from study Visit 1 throughout the study period up to 120 days after the last dose of study therapy. The following are considered adequate barrier methods of contraception: diaphragm, condom (by the partner), copper intrauterine device, sponge, or spermicide. Appropriate hormonal contraceptives will include any registered and marketed contraceptive agent that contains an estrogen and/or a progestational agent (including oral, subcutaneous, intrauterine, or intramuscular agents).

Subjects should be informed that taking the study medication may involve unknown risks to the fetus (unborn baby) if pregnancy were to occur during the study. In order to participate in the study they must adhere to the contraception requirement (described above) for the duration of the study and during the follow-up period. If there is any question that a subject will not reliably comply with the requirements for contraception, that subject should not be entered into the study.

7.83 Use in Pregnancy

If a subject inadvertently becomes pregnant while on treatment with pembrolizumab, the subject will immediately be removed from the study. The site will contact the subject at least monthly and document the subject's status until the pregnancy has been completed or terminated. The outcome of the pregnancy will be reported to ACCRU without delay and within 24 hours. If the outcome is a serious adverse experience (e.g., death, abortion, congenital anomaly, or other disabling or life-threatening complication to the mother or newborn).

The study investigator will make every effort to obtain permission to follow the outcome of the pregnancy and report the condition of the fetus or newborn to the Sponsor. If a male subject impregnates his female partner the study personnel at the site must be informed immediately and the pregnancy recorded on the CRF.

7.84 Use in Nursing Women

It is unknown whether pembrolizumab is excreted in human milk. Since many drugs are excreted in human milk, and because of the potential for serious adverse reactions in the nursing infant, subjects who are breast-feeding are not eligible for enrollment.

8.0 Dosage Modification Based on Adverse Events

8.1 Dose Levels

No dose level adjustments are recommended for any adverse reaction, but the dosing interval may be increased by 1 week if required.

8.2 Dose Modification

Adverse events (both non-serious and serious) associated with pembrolizumab exposure may represent an immunologic etiology. These adverse events may occur shortly after the first dose or several months after the last dose of treatment. Pembrolizumab must be withheld for drug-related toxicities and severe or life-threatening AEs as per **the table below**.

Dose Modification Guidelines for Drug-Related Adverse Events. Use the NCI Common Terminology Criteria for Adverse Events (CTCAE) v. 4.03

CTCAE System/Organ/Class (SOC)	Adverse Event/Toxicity	Hold Treatment For Grade	Timing for Restarting Treatment	Discontinue Subject
Gastrointestinal disorders	Diarrhea/Colitis (8.4)	2-3	Toxicity resolves to Grade 0-1.	Toxicity does not resolve within 12 weeks of last dose or inability to reduce corticosteroid to 10 mg or less of prednisone or equivalent per day within 12 weeks.
		4	Permanently discontinue	Permanently discontinue
Investigations	Increased AST ALT, or Bilirubin	2	Toxicity resolves to Grade 0-1	Toxicity does not resolve within 12 weeks of last dose.
		3-4	Permanently discontinue (see exception below) ¹	Permanently discontinue
Metabolism and nutrition disorders	Hyperglycemia (8.5)	2-3	Toxicity resolves to Grade 0-1	Toxicity does not resolve within 12 weeks of last dose or inability to reduce corticosteroid to 10 mg or less of prednisone or equivalent per day within 12 weeks.
		4	Permanently discontinue	Permanently discontinue
Endocrine disorders	Hyperthyroidism/ Hypothyroidism (8.7)	3	Toxicity resolves to Grade 0-1	Toxicity does not resolve within 12 weeks of last dose or inability to reduce corticosteroid to 10 mg or less of prednisone or equivalent per day within 12 weeks.
		4	Permanently discontinue	Permanently discontinue
	Other: Hypophysitis (8.6)	2	Withhold	Administer corticosteroids and initiate hormonal replacements as clinically indicated Monitor for signs and symptoms of hypophysitis (including hypopituitarism and adrenal insufficiency)
		3-4	Withhold or permanently discontinue	
General disorders and administration site conditions	Infusion Reaction (8.9)	3-4	Permanently discontinue	Permanently discontinue

CTCAE System/Organ/Class (SOC)	Adverse Event/Toxicity	Hold Treatment For Grade	Timing for Restarting Treatment	Discontinue Subject
Respiratory, thoracic and mediastinal disorders	Pneumonitis (8.3)	2-4	Permanently discontinue	Permanently discontinue
Renal and urinary disorders	Renal Failure or Nephritis (8.9a)	2	Toxicity resolves to Grade 0-1	Toxicity does not resolve within 12 weeks of last dose or inability to reduce corticosteroid to 10 mg or less of prednisone or equivalent per day within 12 weeks.
		3-4	Permanently discontinue	Permanently discontinue
Cardiac disorders	Myocarditis	1-2	Withhold	Based on severity of the AE administer corticosteroids. Ensure adequate evaluation to confirm etiology and/or exclude other causes
		3-4	Permanently discontinue	Permanently discontinue
	All other immune-related AEs	2	Withhold	Based on type and severity of AE administer corticosteroids Ensure adequate evaluation to confirm etiology and/or exclude other causes
		3	Withhold or discontinue based on the type of event; Events that require discontinuation include and not limited to: Guillain-Barre Syndrome, encephalitis	
			Recurrent grade 3	
		4	Permanently discontinue	
	All Other Drug-Related Toxicity ²	3 (Severe)	Toxicity resolves to Grade 0-1	Toxicity does not resolve within 12 weeks of last dose or inability to reduce corticosteroid to 10 mg or less of prednisone or equivalent per day within 12 weeks.

CTCAE System/Organ/ Class (SOC)	Adverse Event/ Toxicity	Hold Treatment For Grade	Timing for Restarting Treatment	Discontinue Subject
		4	Permanently discontinue	Permanently discontinue
Note: Permanently discontinue for any severe or Grade 3 drug-related AE that recurs or any life-threatening event. ¹ For patients with liver metastasis who begin treatment with Grade 2 AST or ALT, if AST or ALT increases by greater than or equal to 50% relative to baseline therapy should be held up to 3 weeks. If this does not resolve to grade 2, therapy should be discontinued. Steroids can be used to treat elevated AST/ ALT (see section 8.7). Resolution to grade 2 with steroid treatment will be allowed continuation on therapy. ² Patients with intolerable or persistent Grade 2 drug-related AE may hold study medication at physician discretion. Permanently discontinue study drug for persistent Grade 2 adverse reactions for which treatment with study drug has been held, that do not recover to Grade 0-1 within 12 weeks of the last dose.				

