3.0 Patient Eligibility

3.1 Inclusion Criteria

3.11 Patients must have biopsy-proven adenocarcinoma of the small bowel at any site (duodenum, jejunum, ileum), excluding ampullary and appendiceal tumors.

3.12 Have locally advanced (unresectable) or metastatic small bowel adenocarcinoma.

3.13 Willing and able to provide written informed consent for the trial.

3.14 Age \geq 18 years.

3.15 Measurable disease based on RECIST 1.1.

3.16 Had at least one prior line of systemic chemotherapy for metastatic disease. Adjuvant therapy would not count toward first-line therapy unless patient recurs less than 6 months after completion of that regimen.

3.17 Willing to provide blood and tissue (can be archival) samples for mandatory research purposes (see sections 4.0, 14.0 and 17.0).

3.18 ECOG Performance Status (PS) 0 or 1. (Form is available on the ACCRU web site)

3.19a The following laboratory values obtained \leq 28 days prior to registration.

- Absolute neutrophil count (ANC) \geq 1500/mm³ ($1.50 \times 10^9/L$)
- Platelet count \geq 100,000/mm³ ($100 \times 10^9/L$)
- Hemoglobin \geq 9.0 g/dL (5.6 mmol/L or 90 g/L) without transfusion or EPO dependency (within 7 days of assessment)
- Serum total bilirubin \leq 1.5x upper limit of normal (ULN) **OR** direct bilirubin \leq ULN for subjects with total bilirubin levels $>$ 1.5x ULN
- Aspartate transaminase (AST) and alanine aminotransferase (ALT) \leq 2.5x ULN **OR** \leq 5x ULN for subjects with liver metastases
- Serum creatinine \leq 1.5x upper limit of normal (ULN)
OR
- Measured or calculated creatinine clearance must be \geq 60 mL/min for subjects with creatinine levels $>$ 1.5 X ULN using the Cockcroft-Gault formula below (Glomerular Filtration Rate [GFR] \geq 60 mL/min (1.0 mL/s/m²) can also be used in place of creatinine or CrCl):

Cockcroft-Gault Equation:

$$\text{Creatinine clearance for males} = \frac{(140 - \text{age})(\text{weight in kg})}{(72)(\text{serum creatinine in mg/dL})}$$

$$\text{Creatinine clearance for females} = \frac{(140 - \text{age})(\text{weight in kg})(0.85)}{(72)(\text{serum creatinine in mg/dL})}$$

3.19b Female subject of childbearing potential have a negative urine or serum pregnancy ≤ 7 days prior to registration. If the urine test is positive or cannot be confirmed as negative, a serum pregnancy test will be required.

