8.8 Hepatitis or Hepatic function decline

For **Grade 2** events, monitor liver function tests more frequently until returned to baseline values (consider weekly).

- Treat with IV or oral corticosteroids

For **Grade 3-4** events, treat with intravenous corticosteroids for 24 to 48 hours.

- When symptoms improve to Grade 1 or less, a steroid taper should be started and continued over no less than 4 weeks.

8.9a Renal Failure or Nephritis

For **Grade 2** events, treat with corticosteroids.

For **Grade 3-4** events, treat with systemic corticosteroids.

- When symptoms improve to Grade 1 or less, steroid taper should be started and continued over no less than 4 weeks.

8.9b Management of Infusion Reactions: Signs and symptoms usually develop during or shortly after drug infusion and generally resolve completely within 24 hours of completion of infusion. The table below shows treatment guidelines for subjects who experience an infusion reaction associated with administration of pembrolizumab (MK-3475).

Infusion Reaction Treatment Guidelines

NCI CTCAE Grade	Treatment	Premedication at subsequent dosing
Grade 1 Mild reaction; infusion interruption not indicated; intervention not indicated	Increase monitoring of vital signs as medically indicated until the subject is deemed medically stable in the opinion of the investigator.	None

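### Section 8.2, footnote 1: the liver-metastasis exception opens on a percentage rise but closes on a grade, so the action for some AST/ALT rises is undefined or contradictory

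*Combined protocol and SAP*

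**What the plan says.** Section 3.19a admits patients with AST/ALT up to "5x ULN for subjects with liver metastases", so patients with clearly raised values can enter.

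The Section 8.2 table then handles drug-related rises by grade. Grade 2 AST, ALT or bilirubin is held until Grade 0-1, and treatment ends if that is not reached within 12 weeks of the last dose. Grade 3-4 reads "Permanently discontinue (see exception below".

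The exception is footnote 1. Its population is given as "For patients with liver metastasis who begin treatment with Grade 2 AST or ALT". Its trigger is "if AST or ALT increases by greater than or equal to 50% relative to baseline therapy should be held up to 3 weeks". Its outcome is set by grade: "If this does not resolve to grade 2, therapy should be discontinued", and "Resolution to grade 2 with steroid treatment will be allowed continuation on therapy". For steroids it sends the reader to Section 8.7.

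The table Note adds: "Permanently discontinue for any severe or Grade 3 drug-related AE that recurs or any life-threatening event". Section 8.8, on hepatitis and hepatic function decline, says: "When symptoms improve to Grade 1 or less, a steroid taper should be started and continued over no less than 4 weeks".

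**The concern.** The footnote enters on one scale (percent change from baseline) and leaves on another (grade), and it hangs on a row defined by grade. The two scales need not agree for a patient who already starts at Grade 2. It is then unclear what a site should do when such a patient crosses into Grade 3 on a modest rise, or rises by half without leaving Grade 2.

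At stake is a stop-or-continue decision for hepatic toxicity. Two sites reading the same table could permanently stop one patient and continue another with the same values.

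**Working it through.** The plan prints no figure for this rule, so there is nothing to reproduce. The check is logical, with simple arithmetic.

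**Inputs.** The Grade 2 row, Grade 3-4 row, footnote 1 and Note are from Section 8.2; the entry limit of 5 x ULN is from Section 3.19a. Grading is by CTCAE v4.03, whose cut-points the documents do not print. For illustration only, I assume Grade 2 is above 3 and up to 5 x ULN, and anything above 5 x ULN is Grade 3 or higher. No Grade 3/4 cut-point is needed, because both grades share one row.

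**1. General result.** Let U be the upper limit of Grade 2, b the baseline (b no higher than U) and r the proportional rise.
- The patient leaves Grade 2 when r > U/b - 1.
- The footnote is not triggered when r < 0.5.
- Both can hold when U/b - 1 < 0.5, that is, when b > U/1.5 = 0.667U.

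This is true for any U: the threshold is 2.67 for U = 4, 3.33 for U = 5 and 4.0 for U = 6.

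**2. Illustration, baseline 4.5 x ULN, U = 5.** Grade 2 is left at a rise above 5/4.5 - 1 = 11.1%.

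| Rise | Value (x ULN) | Footnote as an exception to the 3-4 row | Footnote as a replacement for the grade rows |
|---|---|---|---|
| 20% | 4.5 x 1.2 = 5.4 | Not triggered: permanent stop | Not triggered: no action stated |
| 50% | 4.5 x 1.5 = 6.75 | Hold; continue if back to Grade 2 | Same |
| 100% | 4.5 x 2.0 = 9.0 | Hold; continue if back to Grade 2 | Same |

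The readings part in the first line: one stops treatment permanently, the other lets it go on.

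**3. Extent.** With U = 5 the gap exists for baselines above 3.33 x ULN, which is (5 - 3.33)/(5 - 3) = 83% of the width of the assumed Grade 2 band. At a baseline of 5 x ULN it covers every rise above 0% and below 50%. This is a share of the band, not of patients.

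**4. Lower end of the band.** At a baseline of 3.1 x ULN, a 50% rise gives 3.1 x 1.5 = 4.65, still Grade 2; leaving Grade 2 takes more than 5/3.1 - 1 = 61.3%. The hold is triggered, but its release condition (Grade 2) is already met. The Grade 2 row carries no footnote marker and asks for Grade 0-1 within 12 weeks, against Grade 2 and up to 3 weeks in the footnote.

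**5. Neighbouring text.** The footnote marker sits on the combined 3-4 row, while the Note stops treatment for any life-threatening event; no order of precedence is given. Section 8.7 is hyperthyroidism and hypothyroidism; hepatic management is Section 8.8.

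**The case against.** The best reply is that footnote 1 opens by naming a population and so supplies the whole rule for it: nothing below a 50% rise, a hold at 50% or more. On that reading a larger rise is never treated more leniently than a smaller one. The Grade 2 row lends support, since requiring Grade 0-1 would ask these patients to improve on their own baseline. This reply has force, but the text calls the footnote an exception to the Grade 3-4 row and nowhere says that it supersedes the grade rows. It also leaves in place the hold that is already releasable, the unranked Note and the wrong cross-reference.

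Other replies stand in part:
- The table covers drug-related events, and Section 9.1 applies the treatment guidelines when the investigator judges the event related. A small drift in a patient with liver metastasis may not be so judged. That narrows the group, but two drug-related rises from one baseline still meet the problem.
- Because 3 weeks is a maximum, a hold within Grade 2 can be carried out, if only briefly.
- The Note can be read as an overriding stop. A reader might infer that the exception allows re-dosing after a Grade 4 event; the documents do not establish that, and only the precedence is missing.
- The Section 8.8 taper is keyed to symptoms, while the footnote is keyed to AST/ALT. A conflict there is arguable, not shown.

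**Conclusion.** The point holds as an ambiguity in a safety rule. For any Grade 2 upper limit, a baseline above two thirds of it can enter Grade 3 on a rise under 50%. The literal reading then stops treatment permanently, and the replacement reading does not. The general result needs no CTCAE cut-point; only the worked values rest on the assumed band of above 3 to 5 x ULN.

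A reader might go further and infer that the plan plainly stops the smaller rise and restarts the larger one. The documents do not support that without qualification. The larger rise continues only if it resolves to Grade 2 after a hold of up to 3 weeks and is otherwise discontinued, and the replacement reading removes the reversal altogether.

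Nor do the documents support a claim that the response result is biased. They give no frequency for such patients among the planned 41, and under Section 16.2 eligible, consented patients who have begun treatment stay evaluable. The stated sample size, alpha and power are unaffected.

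**What to change.** The sponsor should reconcile footnote 1 with the Grade 2 row, the Grade 3-4 row and the table Note, so that every patient with liver metastasis and a Grade 2 baseline falls under one unambiguous action. The text should:
- say whether the footnote adds to or replaces the grade rows;
- cover expressly a rise under 50% that enters Grade 3, and a rise of 50% or more that stays in Grade 2;
- state whether the footnote or the Note prevails for a life-threatening event;
- correct the steroid cross-reference from Section 8.7 to Section 8.8, and check the Section 8.8 taper wording against these patients' Grade 2 baseline.

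The clinical rule itself is the sponsor's choice. The cost is a wording change in the next amendment and a memo to sites, with no added procedures or patients.
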